### Dose, Frequency, and Administration of the Intervention

Subjects will receive one bottle of a 9-month supply of a vitamin D dose depending on the arm they are randomized to and contingent on their preference for moderate vs. high vitamin D dose. At the end of the study, subjects will be asked to discard any remaining pills in their bottle given that some subjects participate for 3-6 months of follow-up if recruited after October 1, 2022. A low-dose treatment arm (400 IU) will be compared with those in the moderate (4,000 IU/day) to high (10,000 IU/day) treatment arm. Subjects will retrieve blinded bottles containing a 9-month supply of vitamin D at the DCAM pharmacy if they live or work closer to UCM, and at the Rush University Professional Office building, [name] if they live or work closer to Rush. In the event subjects are unable to pick up their vitamin D bottles in these physical locations, bottles will be mailed to an address they provide. The source of the intervention will be the University of Chicago Investigational Drug Service where the bottles will be distributed to DCAM and [name]'s lab at Rush.

**1) Dosing.** The proposed trial will compare high dose (10,000 IU/d) or moderate dose (4,000 IU/d) to low dose (400 IU/d) vitamin D as opposed to lower doses, e.g., 2,000 IU/d maximum dose in the Harvard trial. Schwartz et al. (left panel below) show that 800 or 2000 IU/d produce average levels of only about 35 ng/ml compared to 40-45 ng/ml for 4000 IU/d and 55 ng/ml for 50,000 IU/week. Data from McCullough et al. (Panel A, B below) shows that long-term administration of 10,000 IU/d produces much higher steady state vitamin D levels (about 95 ng/ml) compared to 5000 IU/d, producing about 60 ng/ml. Given the data discussed above on uncertainty about the optimal vitamin D intake/levels for immune function, this innovation in our proposed trial is potentially highly significant.

**2) Safety for higher dosing.** As stated above, there is strong evidence that safety risks up to 10,000 IU/d are minimal. Nevertheless, our study provides both frequent lab monitoring for side effects and education to enable subjects to recognize and respond to any symptoms of side effects if they occur. We also screen out participants with co-morbidities that predispose them to adverse outcomes from higher dose vitamin D supplementation. We have another vitamin D/COVID-19 study in progress with medically complex patients that will provide data on effectiveness and safety under intensive monitoring in that population.

### Procedures and Materials

Blood labs will be taken from subjects at intake, 3 months, 6 months and, if in the 9-month cohort, 9 months. If subjects are in the 2023 cohort (defined as recruited on or after January 1, 2023) blood labs will be taken from

subjects at intake, 3 months, and, if they are recruited in January or February 2023, they will have one final blood draw in June 2023. Labs for UCM subjects will be drawn at DCAM phlebotomy, River East phlebotomy, or Ingalls Hospital, depending on the location most convenient for the subject. Labs for Rush subjects will be drawn by [name] at his Rush lab.

Intake labs will measure baseline calcium and PTH levels, presence of COVID-19 antibodies, baseline vitamin D levels, and vitamin A levels. Where possible given constraints related to sample storage, analysis and available funding for free vitamin D measurement, vitamin D measurements will include free vitamin D levels measured by ELISA assay, as well as total vitamin D levels.

For Aim 7, Intake labs for UCM subjects will additionally measure vitamin D-binding protein (DBP), RAS components (Renin, Ang II, soluble ACE and ACE2), bradykinin, inflammation markers (IL-6, TNF- $\alpha$ , IL-1 $\beta$  and CRP), and SARS-CoV-2 antibodies against S-protein and N-protein.

Follow-up labs (excluding the final lab) will measure PTH levels, calcium levels, vitamin A levels for those who have high baseline vitamin A, and vitamin D levels for monitoring of the intervention's safety and outcomes, and COVID-19 antibodies for monitoring of the outcome. Records of these levels will be kept by the UCM and RU PIs and laboratories.

Final labs will measure calcium levels, vitamin D levels for monitoring of the intervention's safety and outcomes, and COVID-19 antibodies for monitoring of the outcome. Records of these levels will be kept by the UCM and RU PIs and laboratories. Final labs will not measure PTH levels. During the intervention period, our study monitors PTH levels for active participants, because primary hyperparathyroidism is a risk factor for vitamin D toxicity. Given that participants will no longer be taking study-provided vitamin D after their final lab draw, we do not believe it is medically necessary or an appropriate use of limited study resources to continue checking PTH levels with this final draw.

Those who enroll in March 2023 will have baseline labs in March 2023 and final labs in June 2023 (3 months later). This is due to the end of study funding in June 2023. This is further specified in Section IV, Table 4 below.

Testing for calcium, PTH, and vitamin D will be done at UCM (UCMC, River East, or Ingalls) or Rush ([name]'s lab), with the site for each subject selected based on which site is most convenient for the subject. Vitamin A, which will be drawn only from UCM subjects, will be sent to an outside lab for analysis. Throughout the study period we will tell subjects about calcium, PTH and vitamin D lab results only if they suggest a safety concern for which we would like them to seek care from a medical professional. Except in the instance of a safety concern, subjects will be blinded to their vitamin A & D levels, calcium and PTH throughout the study to ensure protocol compliance. At the end of their time in the study, we will provide test results to subjects as indicated in "Study Completion Email V4". At the end of the intervention period for all participants in this protocol, we will unblind participants to their vitamin D dose assignment as indicated in "Dose Unblinding Email V1". We will do this at the end of the intervention for all participants because we, as the study team, are also currently blinded to dose assignments until the end of the intervention period for all participants. For participants who transition to participate in protocol 20-0847, unblinding will occur at the end of the intervention period for all participants in that study. Blood draws for COVID-19 antibodies will also occur at same location as their other lab draws for convenience, consolidated with other labs, but antibody testing will occur at UCM using the Roche assay for consistency given the differing ranges of different COVID-19 assays. Subjects will be instructed during the consent process to seek COVID-19 PCR testing on their own at a site convenient for them if they become symptomatic or were exposed to COVID-19, which is aligned with recommendations from CDC and IDPH. COVID-19 PCR tests will not be part of the research labs, and thus will not be paid for by the study. Subjects will self-report positive COVID-19 PCR results in the quarterly survey. Laboratory records will be monitored regularly by site PIs, Co-Investigators, and members of the DSMB and Clinical Advisory Committee for safety. Patient-reported outcome measures will be measured by a RedCap-based survey.

administered to subjects post-randomization over the phone or via web-based survey at baseline, depending on subject preference, and every 3 months thereafter via a web-based instrument. Subjects will be given the option to call the study team and complete the survey over the phone in reminder emails. Survey and laboratory records will be maintained and monitored by study staff on encrypted, password-protected devices in compliance with UCM and RU IRB Information Security Office standards. Electronic Medical Records will be reviewed for predictors and indicators of COVID-19 and for severity of infection if subject has had a positive COVID-19 test result.

The intake survey will collect baseline data on subjects' current medications and supplements with doses (e.g., multivitamin, zinc, calcium, vitamin D), average time outside per day (specifying direct vs. indirect sun exposure), Fitzpatrick skin type, exercise habits, diet, sleep habits, possible COVID-19 symptoms such as fever, cough, GI problems, and other influenza-like symptoms. Subjects will also be asked to report suspected exposure to the virus (e.g. if a family member falls ill), specific occupation, and demographic information. Subjects will also be asked to evaluate risks of exposure. Participants will also be asked in the intake surveys for the name and contact of information of 1-2 people who could reach them and answer follow-up questions if they cannot be reached or answer questions themselves. Follow-up surveys at months 3, 6, and 9 will ask the participant (or proxy if needed) whether the participant has had a clinically confirmed diagnosis of COVID-19, and the date if so, ask about rates of study medication adherence, and assess for changes in the intake questions about use of other supplements, sun exposure, diet, exercise, and COVID-19 exposures. If the patient is reported to have had COVID-19, we ask about severity, including hospitalization and duration, ICU-use and duration, and need for mechanical ventilation and duration, death and COVID-19 symptom severity using the BEAT-19 adapted to reflect the worst symptomology during their period of active COVID-19. In addition to these questions, we have added some questions on the baseline and follow-up surveys that evaluate additional possible risk factors for COVID-19 outcomes. These risk factors—hypertension, diabetes, and mood—are shown to have possible linkages to vitamin D levels. These factors are receiving increased attention in the context of COVID-19 risk and its relationship to low vitamin D levels. While available evidence suggests there is a link between hypertension/cardiovascular disease, diabetes and metabolism, depression/anxiety, and vitamin D levels, to-date no causal relationship has been established. This is supported by both evidence as recently as this year, as well as earlier studies. Questions about hypertension and diabetes are of our own construction, and questions about depression and anxiety come from validated instruments, the GAD-2 and the PHQ-2. We hope to shed light on the relationship between our outcomes of interest, vitamin D, and these risk factors by asking subjects, both already enrolled and new, about these factors.

For Aims 4-6, we will draw baseline vitamin A for 1,000 UCM subjects and draw vitamin A 3 months later for those UCM subjects who are high at baseline. Of these initial vitamin A samples, we aim to cryopreserve samples from 500 individuals, and perform RNA sequencing on a subset of 100 individuals. Once we reach this number, we will submit an amendment removing these analyses from the consent form and the blood draw/analysis protocol. Because cryopreservation and RNA sequencing involves obtaining 20mLs of additional blood from subjects and involves genetic sequencing, we will ask subjects in the consent form whether they would like to opt-in to provide more blood during their baseline visit for these measurements.

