During the consent process, study participants will be able to choose between being randomized between the low versus high dose strategy or the low dose versus moderate dose strategy. Moderate and high dose treatment participants will be combined for analysis as described below. The moderate and high treatment doses were chosen with help from our clinical advisory committee because they are generally considered safe and potentially effective among persons who meet our inclusion criteria based on medical history and baseline laboratory values (normal calcium and PTH, and negative COVID-19 antibodies). The low dose was selected to ensure that all subjects had a high likelihood of a total vitamin D intake that met the recommended daily allowance (RDA). All patients will be informed of whether their baseline calcium and PTH are normal. Patients who are still eligible for study participation after initial testing will be asked prior to randomization whether they are still willing to participate to maximize retention and minimize dropout. After randomization, subjects will be instructed to pick up their 9-month supply of vitamin D at either UCMC or Rush University corresponding to their randomized, blinded dose. For those unable to pick up their bottles in-person, the UCM IDS pharmacy will mail the subject their bottle. We propose a 3 to 9-month study period, depending on when the subject was recruited, as described in the study timeline of Section IV. Subjects recruited after September 30th will participate in the intervention 6 months to align with study timeline and funding. Subjects enrolled between January 1, 2023 and March 31, 2023 will take the study drug until June 2023, so at least 3 and no more than 6 months. Chart review for subjects will occur for 12 months after the active intervention period has ended. This study timeline is further detailed in Tables 1-4 of Section IV in the currently approved protocol document. Adverse events, defined as hypercalcemia or unexplained increased falls in either study arm will prompt discontinuation of the study medication and further evaluation as reported in the monitoring section below.

[figure not shown]
On the advice of our Clinical Advisory Council faculty members, patients who test for PTH >85pg/dL but have calcium levels <10mg/dL and low vitamin D (<30ng/mL) will be eligible to continue in the study because those

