**Note:** While all participants will receive their final survey invitations in advance of the end of the active intervention date asking them to complete their survey by the study's end date, June 30, 2023, it is possible that some participants may not complete their surveys in time ("overdue participants"). We plan to continue to follow up with overdue participants beyond the study's end date to ensure that participants have the opportunity to complete their final survey. We will do so via multiple modalities (text, email and phone) and at different times of the day to increase response.

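### Unblinding is tied to the trial-wide end of the intervention, so final surveys still outstanding on that date may report the primary outcome after the dose is known

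*Combined protocol and SAP*

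**What the plan says.** The Summary in Section III and Section VII describe the trial as double-blinded. Four parts of the protocol bear on when that ends.

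- **Participants' dose assignment** (Section III, Procedures and Materials): "At the end of the intervention period for all participants in this protocol, we will unblind participants to their vitamin D dose assignment". There is one exception: "For participants who transition to participate in protocol 20-0847, unblinding will occur at the end of the intervention period for all participants in that study".
- **Study team** (same paragraph): they "are also currently blinded to dose assignments until the end of the intervention period for all participants".
- **Laboratory results** (same paragraph): "At the end of their time in the study, we will provide test results to subjects". This runs on each participant's own timeline, not the trial-wide one.
- **Final surveys** (Note after Table 4, Section IV): invitations go out in advance, "asking them to complete their survey by the study's end date, June 30, 2023". For those who miss it: "We plan to continue to follow up with overdue participants beyond the study's end date". Contact is by text, email and phone. No closing date is given.

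The follow-up survey asks whether COVID-19 has been clinically confirmed, and when. Section IX makes that patient report the primary outcome, with viral PCR where available. PCR is not a study test, and Procedures and Materials has participants report positive PCR results through the quarterly survey. The survey is web-based, but participants may call the study team and complete it by phone.

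On records, the Summary says: "Chart review for subjects will occur for 12 months after the active intervention period has ended". Tables 1 to 4 place this in the same period as the final analysis.

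**The concern.** The two timelines meet at 30 June 2023. On that date the condition for the dose email and for ending the team's blinding is met, while the plan still expects some final surveys to come in. Nothing in the available text makes the email wait for an outstanding survey, closes the surveys before unblinding, or masks the people who chase them.

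The primary outcome rests on self-report, and Section VIII enrols people interested in vitamin D as a preventive measure. Someone who learns of a low-dose assignment may be readier to report an illness, and someone who learns of a higher dose less ready. Infections asked about in a late survey will mostly predate unblinding, so the risk is biased recall, reporting or interviewing, not a change in infection itself. The likeliest direction favours the higher doses, though the documents cannot settle that.

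The completion email is a second route. If it carries a vitamin D level and arrives before the last survey, the level may suggest the arm. Section III (Dosing) cites about 35 ng/ml at 800 or 2,000 IU/d, 40-45 at 4,000 IU/d and about 95 on long-term 10,000 IU/d.

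**Working it through.** **Plan's own figure.** The protocol gives none on this point. Its sample-size statement supplies the scale. With 1,000 per arm, 30% control incidence and a hazard ratio (HR) of 0.75, expected events are 1,000 × 0.30 + 1,000 × (1 − 0.70^0.75) = 534.7. Power is Φ(√(534.7/4) × |ln 0.75| − 1.96) = 91.4%, two-sided. This is consistent with the stated minimum of 80%.

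**Who can be exposed.** Nine-month participants enrolled in September 2022, six-month participants enrolled in December 2022, and everyone enrolled from January to March 2023 reach their last survey in June 2023 (Tables 3 and 4). March 2023 enrollees have only that one follow-up survey. Earlier finishers had time to respond while blinded, and are exposed only if their survey was still outstanding at the trial-wide date. Enrolment by month is not given.

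**Size of the bias: an illustration.** Inputs:

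- From the protocol: 1,000 per arm; 30% incidence, so 300 events per arm; 3% per month.
- Derived: a final survey covers three months, so 1,000 × 3% × 3 = 90 events per arm are reported on it.
- Assumed: no true effect; a share f of all final surveys is completed after unblinding; among those, higher-dose participants report a fraction r of their events.

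Reported events in the higher-dose arm are t = 300 − 90 × f × (1 − r). The apparent HR is ln(1 − t/1,000) / ln(0.70). The shift in the test statistic is √((300 + t)/4) × |ln HR|, which gives the two-sided type I error at nominal 5%.

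For f = 10% and r = 0.75, t = 300 − 90 × 0.10 × 0.25 = 297.75. The HR is ln(0.70225)/ln(0.70) = 0.991, the shift is 12.22 × 0.0090 = 0.11, and the type I error is 5.1%.

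Apparent HR (type I error):

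| f | r = 0.90 | r = 0.75 | r = 0.50 |
|---|---|---|---|
| 5% | 0.9982 (5.0%) | 0.9955 (5.0%) | 0.9910 (5.1%) |
| 10% | 0.9964 (5.0%) | 0.9910 (5.1%) | 0.9820 (5.6%) |
| 20% | 0.9928 (5.1%) | 0.9820 (5.6%) | 0.9642 (7.3%) |
| 30% | 0.9892 (5.2%) | 0.9731 (6.3%) | 0.9464 (10.2%) |

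Ten of the twelve cells shift the HR by less than 3%. Because f is a share of the whole trial's final surveys, the lower rows are hard to reach. If 10-50% of participants finish near the end and 20% of those are overdue (both assumed), f is 0.10 × 0.20 = 2% to 0.50 × 0.20 = 10%. The shift is then at most 1.8%, even at r = 0.50.

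**The case against.** The strongest reply is that the exposure is narrow and the outcome fairly hard. Only surveys outstanding at one date matter. The question concerns a dated, clinically confirmed diagnosis, PCR is used where available, and medical records are also reviewed. The protocol gives no send date for the dose email and does not say that overdue participants receive it first, nor that survey staff are handed the allocation list. All of this stands. It limits the size and makes the overlap an inference from timing, but does not close the gap, because the stated rule permits the overlap and nothing prevents it.

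A reader might infer three stronger things that the documents do not support:

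- **That blinding fails for all data collected after 30 June 2023.** Participants moving to protocol 20-0847 stay blinded, and surveys completed on time are unaffected.
- **That post-intervention chart review is equally open to bias.** The Aim 3 items (hospitalization, ICU stay, ventilator use, death) are mostly recorded events, and the plan does not say that post-intervention chart events enter the primary Cox model. For participants finishing by June 2022, the 12-month window closes by June 2023, although abstraction could be done later.
- **That short cohorts show a large distortion.** Among March 2023 enrollees, 20% overdue and low-dose reporting inflated 1.5-fold would give 1/(1 + 0.20 × 0.5) = 0.91. Both inputs are assumptions, and no treatment effect in that month's enrollees is planned. Section IX pools all participants and adjusts for randomization date.

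**Conclusion.** The gap is real but modest. As written, the plan allows the self-reported primary outcome to be collected from some participants after they, and possibly the person taking the survey, know the dose. It does not show that this will happen.

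Under the assumptions above, the pooled hazard ratio moves by about 1-3% or less in most scenarios, with type I error close to 5%. Only a large late share combined with strong differential reporting takes it further, to 0.946 and 10.2% at the extreme. The overdue share and reporting ratio are assumed, since the documents give neither. The two protocol sections removed before review could not be checked. Chart abstraction is a lesser matter. This is worth correcting because prevention is easy and a report made after unblinding cannot be re-blinded, not because the main result is in danger.

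**What to change.** In Section III, Procedures and Materials:

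1. Send the Dose Unblinding Email, and the Study Completion Email where it reports vitamin D levels, only after that participant's final survey is received or a fixed survey cut-off date has passed, whichever comes first. State the cut-off in the Note after Table 4. The later date for protocol 20-0847 participants can stay.
2. Keep dose assignments from staff who contact overdue participants until that cut-off.

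In Section IX:

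3. Record whether each survey was completed before or after unblinding. Use those completed afterwards only in a sensitivity analysis.
4. Say whether post-intervention chart events enter the primary analysis.

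Where existing staffing allows, have charts abstracted without access to the allocation file. This should not be a firm requirement: abstraction runs about a year alongside the final analysis, and full separation could need additional staff.

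The cost is a changed trigger for two emails, restricted access to one file and one extra data field. Some participants learn their dose and results a few weeks later, and a few late surveys leave the primary analysis.

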#### IV. Probable duration

The study period, including recruitment, enrollment, and analysis, will last 36 months. If we are granted a no-cost extension from our funder, NCATS, we expect the recruitment period to last until March 31, 2023, so one year longer, to enroll our target of 2,000 subjects. Once enrolled, subjects' participation will last up to 21 months total. This includes up to 9 months of taking a daily dose of vitamin D, attending laboratory appointments for testing, and answering surveys, and 12 months of chart review thereafter to measure outcomes.

NCATS has granted us an initial no-cost extension to continue the study through June 30, 2022 and our study timeline according to that funding period is specified in Table 1 and Table 2. Given delays in recruitment due in large part to the changing landscape of COVID risk, more infectious variants, the current flu season, and vaccine rollout, we wish to further extend our recruitment period through the end of March, 2023 but this is contingent on an additional no-cost extension from NCATS. We have requested an additional no-cost extension through June 30th, 2023 and anticipate hearing back sometime Spring 2022 with an answer. Should we receive this second extension, we will continue the study through June 2023. In this case, we will adapt to the study timeline specified in Table 3 and Table 4, rather than Tables 1 & 2, specified below. In either scenario, some subjects will participate in our study for 9 months, and others for 3-6 months, depending on when they are recruited to the study (see tables for these dates). Based on our understanding of vitamin D levels in the blood over time including seasonal variation, we believe subjects who participate on treatment for 3 to 6 months will achieve appropriate serum vitamin D levels for analysis. We plan to adjust our analyses for this cohort accordingly.

